Enrollment and informed consent. RAs will enroll and obtain consent from eligible patients for participation in the research activities. The RA will explain the study procedures and incentive schedule, answer any questions, and offer enrollment. Patients will be informed that the decision to participate in the research is voluntary and will not affect the medical care they receive from the ED. If the patient is willing to participate and signs the informed consent form, only then will study staff commence collecting additional information. The informed consent process will be conducted in-person on a study iPad using REDCap (using electronic consent/signature). The participant will be given a paper or e-mailed copy (through REDCap) of the informed consent form and key information sheet. If the patient declines to participate in the study, the RA will call the Relay peer navigator to inform him/her of the patient who has declined to participate in the study but who could potentially receive Relay services (apart from the study, as part of standard DOHMH Relay practice).

Randomization. Patients who meet eligibility criteria and agree to participate in the study will be randomized to the SDC vs. Relay arm. The RA will use an electronic system (REDCap) to create a random assignment to a treatment arm. Randomization uses a 1:1 ratio and is stratified by site; permuted blocks with variable blocks of size 4 and 6 will be used to maintain balance over time and prevent prediction of assignment by the RA. Upon randomization, the RA will immediately inform the participant of the treatment arm assigned. For Relay arm participants, the RA will then inform the Relay peer navigator by phone. If the participant is assigned to the Relay arm, the peer navigator will generally arrive at the ED within 30 minutes.

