Baseline data collection. RAs will administer a baseline self-reported assessment. RAs will also collect participant identifying information to allow future linkage with administrative data, and detailed locator form information to enable study staff to contact participants for follow-up assessments. The locator form collects multiple forms of contact information for the individual (e.g., phone numbers, e-mail, social media, addresses, 'hang out' locations) and phone numbers for at least 3 individuals who will know how to reach them in the future. The locator form is based on procedures used successfully by our team in prior studies, and is a crucial component of the retention strategy. RAs will follow procedures to maximize participant privacy. If at any point during baseline data collection an ED provider needs to provide clinical care to the patient, the RA will pause study procedures so as not to interfere with clinical care.

Because participant identifiers and locator form information are not sensitive to the Relay intervention, RAs can collect this information at the time that is most appropriate to maximize patient flow and ensure

CONFIDENTIAL

This material is the property of the NYU School of Medicine and NYU Langone Health. Do not disclose or use except as authorized in writing by the study sponsor

Behavioral Intervention Template Version: 11 January 2019

peer navigators can engage patients. As much as possible, RAs will complete the baseline assessment prior to participant receipt of the Relay intervention (for participants in the Relay arm).

Administration of Relay intervention or SDC. Relay peer navigators will deliver the ED portion of the Relay intervention for participants in the Relay arm. For participants in the SDC arm, RAs will ensure that, at a minimum, participants receive (from the RA) OEND, a list of treatment programs, and an informational handout about Relay. RAs will document the number of naloxone kits (1-2) distributed as described in Section 14.1. Participants will receive other site-directed care as specific to the particular ED and/or care provider (not under the control of the study). See other sections of this protocol for a detailed description of the Relay intervention and SDC conditions.

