Exit survey. Near the end of the ED stay, the RA will complete an exit survey recording what intervention elements were received by participants. If needed (for example, in instances where the ED visit spans many hours), the RA may complete the exit survey by phone with the participant the day following the ED visit.

Wrap up. RAs will schedule the first follow-up assessment and will give participants a study contact card with the appointment information and information on how to contact the study team. Participants will be given the study incentive payment and a FAQ document about the Greenphire ClinCards. Within the week following the baseline visit the participant will be mailed a thank you card.

Hybrid Baseline visits due to COVID-19

Due to COVID-19, baseline visits may be conducted in a hybrid manner in order to minimize staff time in the ED. In this instance, RAs would screen, enroll, consent, and randomize patients in person in the ED. They would then conduct the survey section of the baseline visit virtually from a private office location adjacent to the ED using iPads (one iPad will be handed to the participant) using video conferencing with a secure, HIPAA compliant platform (WebEx).

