10.4.6 Baseline Descriptive Statistics

Simple descriptive statistics will be examined for baseline characteristics of study participants, as collected on the baseline study survey. Baseline basic characteristics for Relay and SDC arm participants will be compared using bivariate analyses. We expect approximately equal distributions of baseline characteristics for the two study arms given random assignment. Significant differences in baseline characteristics between groups will be adjusted for in outcome analyses.

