10.5 Sample Size

The sample size for this study is 350. Our preliminary data indicate the average number of opioid-related adverse events per year in SDC arm will be in the range of 2-3 events/person; this rate is substantiated in the literature.^{19,50,52,58} We wish to be able to detect a decrease in this number of approximately 25% in the Relay arm, a modest effect size judged to be of public health significance. Using a Poisson regression model for the total number of events, 350 participants provide more than 80% power to detect this difference. Specifically, we have 83% power to detect a decrease in the mean event rate from 2.0 per year in SDC to 1.52 in Relay (an incidence rate ratio (IRR) of 1.32 and a 24% reduction). If average opioid-related adverse events in the SDC arm are lower than anticipated, we still have 80% power to detect a decrease in the mean event rate from 1.75 per year in SDC to 1.32 in Relay (IRR = 1.33; a 25% reduction). All calculations assume a two-sided, 0.05-level test, and conservatively include adjustment for possible overdispersion in the primary outcome (overdispersion parameter = 1.6). While formal power and sample size calculations were based on our primary outcome, given that secondary outcomes are generally more common than our primary outcome (e.g., all-cause ED visits) or are time to events expected not to be rare (e.g., time to opioid-involved OD), we expect to have adequate power for secondary outcome analysis as well.

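### Baseline survey items collected after the arm is disclosed can enter the outcome models as covariates, chosen because they differ between arms

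*Combined protocol and SAP*

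**What the plan says.** **Order of events.** Section 7.3.1 describes consent and then randomisation, with "Upon randomization, the RA will immediately inform the participant of the treatment arm assigned". For the Relay arm the research assistant (RA) next phones the peer navigator, who generally arrives within 30 minutes. The paragraph on baseline data collection follows. Section 7.1 lists randomisation ahead of the research interviews. For the hybrid COVID-19 visit the order is explicit: patients are randomised in the ED, and of the RAs the text says "They would then conduct the survey section of the baseline visit virtually". Section 10.6.1 states that the RA doing the baseline assessment cannot be blinded.

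**Timing against Relay.** Section 7.3.1 says that identifiers and the locator form are not sensitive to Relay and may be collected whenever convenient. For the survey it says "As much as possible, RAs will complete the baseline assessment prior to participant receipt of the Relay intervention".

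**Content.** Section 4.2.2 has MOUD in the past 90 days asked at baseline. Section 10.4.2 has the overdose questionnaire given at each study visit.

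**Use in analysis.** Section 10.4.6 takes baseline characteristics from the baseline survey and says "Significant differences in baseline characteristics between groups will be adjusted for in outcome analyses". Section 10.4.2 adjusts the primary model for site and for other baseline factors that may be unbalanced. Neither section limits covariates to values that assignment cannot affect.

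**The concern.** A covariate is safe to adjust for when treatment assignment cannot have influenced it. Self-reports given to an unblinded interviewer, by a participant who already knows the arm and may occasionally have met the peer navigator, do not carry that guarantee. If assignment moves the answer, adjusting for it removes or adds part of the arm difference.

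The selection rule makes this worse. An item enters the model because the arms differ on it, and a shift caused by assignment is one way for the arms to differ. The rule also means that the final model is chosen by the data and cannot be fully prespecified. At stake is the adjusted arm contrast in the primary rate-ratio model and in the secondary models that Section 10.4.3 builds on the same pattern.

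**Working it through.** **The plan's own figures.** The plan gives no figure for this point. Its only design calculation is power: "The sample size for this study is 350", "Randomization uses a 1:1 ratio and is stratified by site", "All calculations assume a two-sided, 0.05-level test", and "we have 83% power to detect a decrease in the mean event rate from 2.0 per year in SDC to 1.52 in Relay", with overdispersion 1.6. A Wald calculation on the log rate ratio with 175 per arm gives

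- SE = sqrt(1.6 × (1/(175 × 2.0) + 1/(175 × 1.52))) = 0.103
- ln(1.52/2.0) = ln(0.76) = −0.274
- power = Φ(0.274/0.103 − 1.96) = 76%

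The most favourable two-sided variant tried, a Poisson-regression formula with SDC as base, gives 80.1%. The stated 83% was not reproduced under the stated settings. That is a separate matter, and nothing below depends on it.

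**Inputs for this check**

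- From Sections 10.5 and 7.3.1: 175 per arm, rates 2.0 and 1.52 (Relay:SDC ratio 0.76).
- From Section 10.4.6: adjust if the arms differ significantly. I take this as two-sided p < 0.05 (assumption; the section gives no threshold).
- Assumed, as the documents give neither: shift d of 0.1 to 0.2 SD in a baseline item; correlation r = 0.5 with a continuous outcome, or log-rate slope b = 0.4 per SD for the count outcome.

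**Step 1: how often the item is selected.** The observed arm difference D in the item has SE sqrt(2/175) = 0.107 SD. With m = d/0.107, the selection probability is Φ(m − 1.96) + Φ(−m − 1.96).

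| d (SD) | m | Selected |
|---|---|---|
| 0 | 0 | 5% |
| 0.1 | 0.94 | 15% |
| 0.2 | 1.87 | 46% |

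**Step 2: average bias on a continuous outcome.** Adjustment subtracts r × D, but only when the item is selected. The average bias is r × E[D × 1(selected)], where the expectation is 0.107 × {m[Φ(m − 1.96) + Φ(−m − 1.96)] + φ(1.96 − m) − φ(1.96 + m)}.

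- d = 0.1: expectation 0.040; bias 0.5 × 0.040 = 0.02 SD
- d = 0.2: expectation 0.135; bias 0.5 × 0.135 = 0.07 SD

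**Step 3: primary count model.** By the same argument the log rate ratio moves by b × E[D × 1(selected)] on average. If Relay participants report lower risk (d negative):

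- |d| = 0.1: 0.76 × exp(0.4 × 0.040) = 0.77
- |d| = 0.2: 0.76 × exp(0.4 × 0.135) = 0.80

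Simulation of the rule (350 participants, SDC rate 2.0, variance 1.6 times the mean, 1000 replicates) gives the same 0.77 and 0.80. With slopes of 0.2 to 0.6 in place of 0.4, the formula gives 0.77 to 0.78 at |d| = 0.1 and 0.78 to 0.82 at |d| = 0.2. If disclosure shifts reporting the other way, the sign reverses: 0.76 × exp(−0.016) = 0.75 and 0.76 × exp(−0.054) = 0.72, which exaggerates benefit.

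**Step 4: with no shift.** The simulated adjusted rate ratio is 0.76 to 0.77, so there is no systematic bias. The same holds for covariates fixed before assignment. The sample size is unchanged.

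**The case against.** The best defence is that the protocol already sees the stronger route. It separates forms that Relay cannot affect from those it may affect, and it directs the survey ahead of peer contact where possible. Detailed RA procedures are left to the operating manual, and Section 10.1 calls the analysis approach preliminary. Site is always adjusted for and cannot be shifted. The administrative part of the primary outcome is abstracted blind to arm. All of this stands. It does not protect against knowledge of the arm, and it does not change the covariate rule as written.

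A reader might infer more than the documents support:

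- **That the survey is planned to follow Relay contact.** It is not; that is a fallback. The baseline survey's length is not given. Only if it resembles the 30 to 40 minutes stated for follow-up interviews would it be likely to overlap the peer's arrival.
- **That the order is stated outright for every visit.** It is explicit only for the hybrid visit. For the standard visit it rests on paragraph order and the list in Section 7.1.
- **That the bias is simply correlation times shift, 0.05 to 0.10 SD, to be set against a detectable difference of about 0.30 SD.** That product assumes the item is always adjusted for, whereas Section 10.4.6 adjusts only after a significant difference. The SD benchmark also does not fit a count endpoint.
- **That stigma and motivation are affected, or that the risk-score model starts from a contaminated baseline.** The baseline instrument is a separate attachment, Section 10.4.8 does not say when mediators are measured, and Section 10.4.3 does not say how baseline enters the risk-score model.

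**Conclusion.** The point holds as a possibility that the analysis rule leaves open. The documents do not show that baseline values will be distorted. As written, post-disclosure self-reports may become covariates, and a shift due to assignment raises their chance of selection from 5% to about 15% to 46% for an assumed shift of 0.1 to 0.2 SD. The average effect on the estimate is then modest: about 0.02 to 0.07 SD on a continuous outcome at an assumed correlation of 0.5, or a mean rate ratio of about 0.77 to 0.80 for a true 0.76 at an assumed slope of 0.4 per SD. Direction is unknown. The unadjusted contrast, and adjustment for site, age or sex, are not affected.

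**What to change.** In Sections 10.4.2 and 10.4.6, delete the rule that adjusts for unbalanced or significantly different baseline factors. Prespecify adjustment for site, the stratification factor, plus a short list of traits that assignment cannot alter, such as age and sex. Use survey items collected after randomisation as covariates only in a labelled sensitivity analysis. For that analysis, record the REDCap time of the survey relative to randomisation and, in the Relay arm, to first peer contact.

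This is a cheap improvement. It is mainly wording and needs no extra participants or visits, and Section 10.1 leaves the detailed plan to be finalised before outcome analysis. The cost is some precision if a strongly prognostic self-report is left out of the primary model.

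Moving the sensitive survey block ahead of randomisation would also remove the problem. It would delay the call to the peer navigator, and some patients might leave before randomisation; Section 6.1 notes that patients may be anxious to be discharged. That is a feasibility trade-off for the sponsor to weigh, and the fix above does not depend on it.

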7.3.2 Intermediate Visits

Acceptable time windows are given for each study visit, but attempts will be made to conduct the visit as close as possible to the intended day (+/- 3 days when possible).

Visit 2 (Day 30 +14/-7) (*All participants, conducted by RA or PM)

- RA administers structured interview over the phone or in person (30-40 minutes).
- Study incentive payment added to ClinCard.

Visit 3 (Day 90 +30/-14) (*All participants, conducted by RA or PM)

- RA administers structured interview over the phone or in person (30-40 minutes).
- Study incentive payment added to ClinCard.

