4.2.2 Secondary Study Endpoints

Secondary endpoints include the impact of Relay on the following outcomes:

- Initiation of medication for opioid use disorder (MOUD)
- OD risk behaviors
- Time to next opioid-involved OD
- ED visits for any cause
- ED visits for opioid OD
- ED visits for other substance use reasons
- Self-reported opioid-involved OD

CONFIDENTIAL

We expect that Relay will be effective in increasing MOUD initiation because it is built on a foundation of prior work demonstrating that ED interventions by non-medical staff can effectively link patients to treatment. Measures of MOUD initiation will be gathered at each study visit. MOUD is defined as use of methadone, buprenorphine, or naltrexone that is prescribed by an office-based provider or provided by a treatment program as treatment for OUD. Initiation is defined as receiving MOUD within the 90 days following the index visit, for individuals who received no MOUD for at least 2 weeks prior to the index visit.³⁸ Though infrequent, if patients are initiated on MOUD during the index visit (in the ED or, if admitted from the ED, in the hospital), the first outpatient MOUD encounter post-discharge will be the measure of treatment initiation. We will include MOUD initiated in the ED in sensitivity analyses. Our primary analysis is limited to the individual's first episode of outpatient MOUD in the 90 days (3 months) following enrollment because this is the duration of contact with the Relay peer navigator and thus, for individuals in the Relay arm, is most attributable to the intervention. However, we will measure the total number of MOUD initiation episodes and time receiving MOUD for a full 6 months, to capture any continued intervention effect. Assessments at baseline and follow-up will collect data on MOUD in the past 90 days.

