Fidelity monitoring of intervention: We will assess fidelity as follows: 1) All participants will complete an RA-administered exit survey interview at the conclusion of the baseline visit (in some cases the exit survey may be completed by phone the next day). The exit survey will assess what interventions the participant received in the ED that are relevant to opioid OD (e.g. substance use screening, OD education, naloxone kit(s) received, treatment referral/follow-up offered). The exit survey interview will also ensure that SDC arm participants receive, at a minimum, OEND, a list of treatment programs, and a handout with Relay program information. RAs will need to check off boxes in the exit survey indicating that the participant has received these items. Participants will also be asked at follow-up assessments what additional Relay program services they have received in the interval since the last assessment, 2) After each participant contact, Relay peer navigators complete content checklists to capture the duration of the interaction and activities performed during the session. To minimize burden to DOHMH and the peer navigators, the study will use the existing peer navigator contact content checklists used by DOHMH. Throughout the study, we will use this data to assess intervention dose, measured using the number, type (phone or in-person conversation, accompaniment to appointments), and duration of contacts; this information is routinely logged by the Relay peer navigator for DOHMH, as part of regular program activities. We will obtain a MOU/DUA to use these checklists to assess study fidelity.

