7.3.3 Final Study Visit

Final Study Visit (Visit 4, Day 180 +30/-14) (*All participants, conducted by RA or PM)

- RA administers structured interview over the phone or in person (30-40 minutes).
- Participant is provided with final study incentive payment via ClinCard.
- Any questions about the study are answered and participant is given contact information for the study if needed.

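### The fixed 90-day recall for MOUD does not guarantee that interviews held in window cover the 90-day endpoint or the 6-month measure

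*Combined protocol and SAP*

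**What the plan says.** Section 4.2.2 makes MOUD initiation a secondary endpoint: receipt in the first 90 days after the index visit, among people with no MOUD in at least the two weeks before it. It is gathered at study visits, and the recall is fixed: "Assessments at baseline and follow-up will collect data on MOUD in the past 90 days". The same section adds that "we will measure the total number of MOUD initiation episodes and time receiving MOUD for a full 6 months".

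The interview windows are in sections 7.3.2 and 7.3.3: "Visit 2 (Day 30 +14/-7" (Days 23 to 44), "Visit 3 (Day 90 +30/-14" (Days 76 to 120) and "Visit 4, Day 180 +30/-14" (Days 166 to 210). Staff aim for closer timing, within "3 days when possible". Section 5.7.2 lets a participant skip individual interviews without withdrawing.

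For other items the recall is tied to the previous interview. Section 6.1.2 asks "what additional Relay program services they have received in the interval since the last assessment", and section 5.3.1 asks about incarceration since the preceding visit. Section 10.4.3 analyses 90-day initiation by logistic regression and gives no rule for a participant whose 90 days were only partly covered.

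**The concern.** A fixed 90-day recall covers the follow-up continuously only if completed interviews are close enough together. Visit 3 can be held two weeks before the endpoint closes, and Visit 4 can be held more than 90 days after it. The stretch between Visit 3 and the start of the Visit 4 recall is then asked about at neither interview. A skipped Visit 3 widens that stretch.

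Two things follow. A MOUD episode that starts and ends in the stretch is missed. An episode that continues past it is reported at the next interview, but without a start date it may not be possible to place it before or after Day 90.

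Early and skipped interviews are foreseeable. Section 5.4.1 starts outreach about two weeks before the due date. Section 7.3.5 allows a scheduled interview to be done when a participant returns to the ED with a repeat overdose, if the window is open, so interview timing can depend on an outcome that Relay is meant to change. At stake is a secondary endpoint intended to show whether Relay links patients to treatment.

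**Working it through.** The plan states no figure for coverage, so there is none to reproduce. The check is interval arithmetic.

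**Inputs.** Visit windows from sections 7.3.2 and 7.3.3; 90-day recall and 90-day endpoint from section 4.2.2; permission to skip interviews from section 5.7.2. Baseline is Day 0.

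**Formulas.** An interview on day v covers days v − 90 to v. For consecutive completed interviews on days a and b:

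- whole days unasked = max(0, b − a − 91)
- of these, inside the endpoint = max(0, min(90, b − 91) − a)
- unobserved tail of the 6-month period = max(0, 180 − day of Visit 4)

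Measured as elapsed time rather than whole days, the gap between two interviews is one day longer (for example 14 rather than 13, or 44 rather than 43).

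| Completed interviews (days) | Next recall starts | Days unasked | Count | In the endpoint |
|---|---|---|---|---|
| 90 and 180 (on target) | 90 | none | 0 | 0 |
| 76 and 166 | 76 | none between visits; tail 167–180 | 0 (tail 14) | 0 |
| 76 and 180 | 90 | 77–89 | 13 | 13 (13/90 = 14%) |
| 76 and 210 | 120 | 77–119 | 43 (43/180 = 24%) | 14 |
| 87 and 183 (edge of the 3-day aim) | 93 | 88–92 | 5 | 3 |
| 30 and 180, Visit 3 skipped | 90 | 31–89 | 59 | 59 (59/90 = 66%) |
| 0 and 120, Visit 2 skipped | 30 | 1–29 | 29 | 29 (29/90 = 32%) |

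**How general the gap is.** Visits 3 and 4 each have 45 permitted days, giving 45 × 45 = 2,025 pairs. In 990 the two interviews are more than 90 days apart, and in 525 of those Visit 3 also precedes Day 90. Within the 3-day aim there are 7 × 7 = 49 pairs; 21 are more than 90 days apart, 15 of them with Visit 3 before Day 90. A separation of exactly 91 days is counted here although it leaves no whole day unasked. These are counts of permitted combinations, not probabilities.

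**Other sources.** Sections 4.2.2, 10.4.2 and 14.1 assign administrative data to the primary outcome and the ED-visit endpoints, and section 4.2.3 assigns death records to mortality. None assigns them to MOUD, so nothing in the plan fills the gap.

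**After the change.** With recall running from the last completed interview, the gap between interviews is 0 for every pair and for any skipped visit. A tail of up to 180 − 166 = 14 days remains in the 6-month measure when Visit 4 is early.

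**The case against.** The strongest reply is that the gap is conditional and usually small. That stands. On-target visits leave none, the 3-day aim caps the endpoint loss at 3 days, and 2,025 − 525 = 1,500 permitted pairs leave the endpoint covered between Visits 3 and 4. The largest loss in the table, 59 days, comes from a skipped interview rather than from the window itself. It still belongs to the same point, because the fixed recall stops a completed six-month interview from recovering those days.

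The item wording is in Attachment J (follow-up questionnaires, listed in section 19), which is not among the documents reviewed. Counting episodes and time on MOUD needs some timing data, so dates may already be collected. This also stands, and the remedy is worded accordingly.

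Section 10.1 says that a detailed analysis plan will be finalised before outcome analysis, so a coding rule may yet be written. That answers the missing rule, but a rule cannot recover days that were never asked about.

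A reader might infer that initiations in the gap are scored as no initiation. The documents do not say so; they give no coding rule either way, and an episode still running when the next recall begins is seen. A reader might also infer dilution of the treatment effect, on the ground that late initiations are the ones lost. That is unsupported. A Visit 3 on Day 90 or later covers the late days, a Day 120 interview after a skipped Visit 2 loses the early ones, and no MOUD rates or uptake times are given.

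**Conclusion.** The point holds as a failure to guarantee coverage. With interviews in window, up to 14 endpoint days (13 when Visit 4 is on Day 180) and up to 43 days of the 6-month period can go unasked. With Visit 3 skipped and Visits 2 and 4 on Days 30 and 180, 59 of 90 endpoint days go unasked.

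This rests on reading the section 4.2.2 recall literally and on MOUD having no other data source. It does not support saying that the 6-month measure is unobserved in general. How often gaps would occur, and the size and direction of any bias between arms, cannot be derived from the documents. For one secondary endpoint, this is an inexpensive improvement rather than a threat to the trial's main conclusion.

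**What to change.** 1. At each follow-up, ask about MOUD since the last completed interview, or since the index ED visit if there has been none. The plan already does this for Relay services and incarceration.
2. Record the date of the first outpatient MOUD encounter, and start and stop dates, if Attachment J does not already do so. A Visit 3 held after Day 90 also needs these, because its recall takes in days beyond the endpoint.
3. State the classification rule in section 10.4.3. A dated initiation by Day 90 counts whenever it is reported. A participant is a non-initiator only on the evidence of an interview on or after Day 90, using the six-month interview when Visit 3 was early or skipped. Otherwise the outcome is missing.
4. Express time on MOUD over the days actually observed, because of the tail of up to 14 days.

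Keep the Visit 3 window as it is. Opening it only at Day 90 would remove 14 contact days in a population that is hard to reach, and could turn early interviews into missed ones, which lose more.

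The cost is one reworded questionnaire item, possibly some date fields, and a few lines of analysis text. The downside is longer recall after a skipped visit: 180 − 30 = 150 days for someone seen on Days 30 and 180, with the recall error that brings.
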